## LIST OF ABBREVIATIONS AND DEFINITION OF TERMS

 Zr	Zirconium-89
AE	Adverse Event
BID	Twice Daily
BSA	Body Surface Area
CBC	Complete Blood Count
CI	Confidence Interval
CMAX	Maximum Concentration Of Drug
CNS	Central Nervous System
CRF	Case Report/Record Form
CTCAE	Common Terminology Criteria For Adverse Events
DLT	Dose-Limiting Toxicity
DSMC	Data Safety Monitoring Committee
ECG	Electrocardiogram
ECOG	The Eastern Cooperative Oncology Group
EGFR	Epidermal Growth Factor Receptor
FDA	Food and Drug Administration
GI	Gastrointestinal
GMP	Good Manufacturing Practice
Hgb	Hemoglobin
HNSCC	Head And Neck Squamous Cell Carcinoma
HTN	Hypertensions
ILD	Interstitial Lung Disease
IND	Investigational New Drug
IRB	Institutional Review Board
IV	Intravenous
LLN	Lower Limit Of Normal
MTD	Maximum Tolerated Dose
NIR	Near Infra-Red
NHS	N-hydroxysuccinimide
PLT	Platelet
RBC	Red blood cell
SAE	Serious Adverse Event
SCC	Squamous Cell Carcinoma
TBR	Tumor to Background Ratio
SCCHN	Squamous cell carcinoma of the head and neck
TSH	Thyroid stimulating hormone
UAB	University of Alabama at Birmingham
ULN	Upper Limit Of Normal
UNK	Unknown
WBC	White blood cell
WHO	World Health Organization

## SCHEMA

[figure not shown]

Figure 1. Study overview.

**Study plan.** The study is an open label, single institution, pilot study to determine the distribution pattern of  $^{89}\text{Zr}$ -panitumumab and panitumumab-IRDye800 in subjects with head and neck squamous cell carcinoma (HNSCC) that undergo surgery with lymphadenectomy of curative intent. 30 mg of panitumumab-IRDye800 will be administered 1-5 days prior to surgery, intravenous (IV) over 15 min followed by an observation period of 30 min.  $^{89}\text{Zr}$ -panitumumab will be systemically injected at a dose of 1.0 mCi +/- 20%, and with a specific activity greater than 200 Ci/mmol at the time of injection. The injected mass dose is less than or equal to 1 mg (7 nmol); the subject will be monitored for 1 hour post-administration. If at any point two subjects in a cohort experience a DLT, then the study will stop and safety data will be reviewed. The medical monitor and safety review will occur independently.

There will be 7 subjects enrolled into each cohort (total of 14 subjects in the study) whereby, based on the preoperative work-up, including a physical exam and evaluation of the pre-existing imaging data, subjects will be assigned to the node negative or node positive group.

**Rationale for the two cohorts.** To ensure the inclusion of sufficient subjects with clinically positive lymph nodes, we created a cohort structure. Including both node-positive and node-negative subjects will ensure that we will have tumor-positive nodes when performing the data analysis. Moreover, by analyzing data from node-positive subjects it will become possible to assess if, in case large lymph node metastasis are present, the tracer(s) can still reach the node or if rerouting (a phenomenon known to happen in sentinel node mapping, i.e., drainage to a “false” sentinel node occurs because the “true” sentinel node cannot be reached). As shown in the study schema, all subjects regardless if enrolled in cohort 1 or 2, will undergo the same treatment, and upon data collection statistical analysis will be performed with the pooled data.

## 1. OBJECTIVES

### 1.1. Primary Objective

Determine the sensitivity and specificity of Zr-panitumumab for the detection of tumor-involved regional lymph nodes.

As defined by histological and/or pathological evaluation (gold standard), the total number of tumor-positive nodes will be determined for both Zr-panitumumab and F-FDG-PET imaging findings. The specificity and sensitivity of Zr-panitumumab will be calculated and compared to the specificity and sensitivity of F-FDG for metastatic lymph node identification. Additionally, we will determine the level of association between the Zr-panitumumab-PET results and F-FDG-PET results with the Phi coefficient.

### 1.2. Secondary Objective

Determine the number (proportion) of lymph nodes determined to be tumor-positive by histological and/or pathological evaluation that were NOT predicted tumor-positive by Zr-panitumumab labeling.

We will calculate the odds of a false negative using Zr-panitumumab-PET relative to the odds of a false negative using a F-FDG-PET and compare the negative predictive values of Zr-panitumumab-PET and F-FDG-PET.

### 1.3. Exploratory Objectives

- Determine the sensitivity and specificity of panitumumab-IRDye800 for the detection of tumor-involved regional lymph nodes.

After isolation of lymph nodes from the specimen in the pathology lab, lymph node fluorescence will be measured prior to histological and/or pathological evaluation (gold standard). Sensitivity and specificity will be generated by comparison of fluorescence intensity and histological and/or pathological evaluation (gold standard). Findings will furthermore be compared to the sensitivity and specificity of Zr-panitumumab and F-FDG (primary objective).

- Determine the number (proportion) of lymph nodes determined to be tumor-positive by histological and/or pathological evaluation that were NOT predicted tumor-positive by panitumumab-Irdye800 labeling.

We will measure the level of association between panitumumab-IRDye800 results and Zr-panitumumab-PET and F-FDG-PET results with the Phi coefficient.

- Dosimetry

In a subset of 3-5 subjects, dosimetry data will be collected to determine the toxicity of Zr-panitumumab to the organs.

**NOTE:** It is planned that exploratory objectives will only be reported in publication(s), if any, but not on ClinicalTrials.gov.

## 2. BACKGROUND

The most important determinant of survival for many cancer types is the presence of lymph node metastasis (1-3). In head and neck cancer, nodal metastases reduce 5-year survival to half, regardless of the primary tumor T stage (2-4). Likewise, regional metastases to axillary nodes in breast cancer decreases 5-year survival by approximately one-third (5). Although nodal disease can often be detected on routine physical exam or anatomic imaging with or without metabolic imaging, there are many cases where clinical and radiographic exams are negative, but microscopic disease is identified within the

primary nodal basin. This finding dramatically changes the diagnosis, and as a result, great effort is taken to harvest the first echelon lymph node(s) during removal of the primary tumor. When metastatic disease is too small to be detected preoperatively, this leads to down staging and under treatment.

**Complete nodal dissection causes significant morbidity.** The gold standard for detection of regional metastatic disease in HNSCC traditionally has been a regional nodal dissection that is associated with shoulder dysfunction and pain due to accessory nerve (cranial nerve XI) injury being common after neck dissection (6–9). Moreover, 60% to 80% of subjects undergoing a neck dissection with sectioning of the nerve have pain, limited abduction of the shoulder, and anatomic deformities such as scapular flaring, droop, and protraction (10). To reduce morbidity, there has been a gradual migration away from extensive dissection to more limited dissection offered by sentinel node biopsy where only the primary tumor draining lymph node(s) are removed for detailed histologic examination (5,11–14). Where sentinel node biopsy has already displaced regional lymphadenectomy in melanoma and breast surgery to avoid the associated deficits associated with this more aggressive approach, it is now also advocated for HNSCC (NCCN guidelines, version 1, 2017/2018).

**Sentinel lymph node biopsy** is performed as a surgical staging method to detect occult nodal disease in those tumor types with a high metastatic rate and where lymph node disease predicts outcome and informs adjuvant treatment decisions. The premise of sentinel node surgery is that regional metastasis from the primary tumor occurs through drainage of lymphatics to a single (or several) lymph nodes that can only be defined by mapping at the time of surgery. Sentinel node mapping occurs by local radiotracer or blue dye injection surrounding the primary tumor, thereby identifying the natural lymphatic drainage pattern from the primary tumor directly to the sentinel node(s). Sentinel nodes undergo aggressive histopathologic exam to assess for micro- or macro-metastatic disease.

Meta-analysis of sentinel node dissection in breast cancer, head and neck cancer, and melanoma have validated the accuracy of sentinel node biopsy in predicting occult lymph node metastasis (5,14–16), with a sensitivity of 91% (9) and a 3 to 10% false-negative rate. The false-negative rate can be due to poor injection technique or not anticipating the full extent of disease during injection, but the rerouting and skip metastasis phenomenon's have been postulated here as well (17–19). Moreover, although sentinel node mapping is superior to radiographic and clinical exam, it is still limited by the need for direct injection of the dye or radiolabeled compound. **Upstaging with sentinel node assessment can thus only be assessed in tumor types that are accessible for local injection.** This is significant because it influences standard of care (sentinel node surgery or complete lymphadenectomy) in these subject populations only. Identification of regional disease will inform prognostic information and/or determine the need and extent of adjuvant therapies for additional tumor types. Most importantly however, remains the fact that both lymphadenectomy and sentinel node biopsy do not allow for intraoperative lymph node staging. In both cases, post-operative (histo-) pathological evaluation is required to determine whether or not lymph node metastasis were present in the regional lymph node basin(s). Thus, HNSCC patients would benefit from an alternative technique that, ideally, allows for both preoperative as well as intraoperative lymph node staging.

**Fluorescently labeled antibodies are currently used to target and visualize tumor cells intra-operatively.** The safety and efficacy of cetuximab-IRDye800 were evaluated in the phase 1 clinical trial entitled “Open-label Study Evaluating the Safety and Pharmacokinetics of Escalating Doses of cetuximab-IRDye800 as an Optical Imaging Agent to Detect Cancer During Surgical Procedures,” (incorporated to IND by cross-reference). A second phase 1 clinical trial is currently in progress, and is entitled “Open-label Study Evaluating the Safety and Pharmacokinetics of Escalating Doses of

Panitumumab-IRDye800 as an Optical Imaging Agent to Detect Head and Neck Cancer During Surgical Procedures" (IRB-35064, incorporated to IND by cross-reference).

**This clinical trial is proposed to determine if a systemic injection of tracer labeled antibody will specifically accumulate in tumor containing lymph nodes to enhance identification.** If successful, we will leverage existing technologies, PET and fluorescently labeled antibodies, in order to expand regional lymph node assessment to cancer types where direct injection is not possible.

## **2.1 Study Disease**

This study is being performed in head and neck squamous cell carcinoma (HNSCC). Because the standard of care in this setting is currently complete lymphadenectomy, our proposed method will allow direct comparison with conventional lymphadenectomy and thus calculation of false positive and negative rates, sensitivity and specificity. Potential expansion to other cancer types not readily accessible for tracer injection, e.g., ovarian, uterine, and pancreatic cancer, are possible after showing the feasibility and validity of the approach in this study.

## **2.2 Study Agents**

The study agents for this trial are **Zr-panitumumab** and **panitumumab-IRDye800**.

### **2.2.1 Zr-panitumumab**

Zr-panitumumab is a conjugate of Zr, the radioactive isotope of zirconium (Zr), and panitumumab, the fully-humanized anti-epidermal growth factor receptor (anti-EGFR) IgG2 monoclonal antibody approved by FDA as Vectibix. The approved single agent indication for Vectibix is treatment of metastatic colorectal carcinoma with disease progression. See Section 5.1.1 for more information.

### **2.2.2 Panitumumab-IRDye800**

Panitumumab-IRDye800 is a conjugate of panitumumab and IRDye® 800CW N-hydroxysuccinimide (NHS) ester infrared dye (LI-COR Biosciences, Inc., Lincoln, NE). See Section 5.1.2 for more information regarding panitumumab-IRDye800.

## **2.3 Rationale**

### **Overall Impact of proposed studies on surgical oncology**

Upstaging with sentinel node assessment has only been assessed in tumor where the tumors are accessible for local injection. We plan to determine if additional tumor types are amenable to regional lymph node staging after systemic injection of tracer labeled antibody. Identification of a novel lymph node detection methodology has the potential to 1) increase the sensitivity and decrease the false negative rate by avoiding the variability of direct injection; and 2) allow study of lymph nodes within non-superficial cancer types that are known to metastasize such as prostate, ovarian, uterine, lung and pancreatic cancers.

Although this study assesses an EGFR-directed antibody, this work, if successful, would have implications for any large protein-based imaging strategy. Currently, at least 12 such trials exist on ClinicalTrials.gov.

**The methodology of this study and future studies could dramatically improve the standard of care in the following ways:**

- 1) Non-invasive detection of subclinical disease may allow improved subject selection for surgery as well as provide the surgeon with a roadmap for planning the surgical procedure.**
- 2) Detect subclinical disease in the operating room at the time of resection:** Accurate identification of nodes may identify metastasis not detected by PET, and early identification of metastasis will improve survival.
- 3) Real time feedback provided the radioactive and fluorescence signatures of the tracers:** Combined use could ultimately improve both the sensitivity and specificity of metastatic cancer detection and the ability to accurately resect it.
- 4) Reduction of surgery time:** Although outside the scope of this study, successful identification of nodes in the clinic may reduce surgery time by reducing the need for complete nodal resection, reducing surgery time by up to 40 minutes. This might reduce the time subject is in surgery, and the cost of the surgery.
- 5) Increased survival rate:** Replacing complete nodal resection as the standard of care with tumor-directed node resection might decrease the negative effects that accompany complete resection, and might also improve survival rate.
- 6) This is the first-in-human dual modality study involving Zr-panitumumab and panitumumab-IRDye800 for regional lymph node staging specifically focusing on the identification of tumor-loaded lymph nodes.** However, promising results might lead to expansion of this methodology to **use in other cancer types.** Intravenous injection of antibody-labeled radiotracers would allow regional lymph node staging in other cancer types where local injection is not possible. This would tremendously broaden the application to those indications for which lymph node staging is considered of great prognostic value (eg, gynecological, urological).

## **2.4 Study Design**

### **For clinicaltrials.gov and Stanford Clinical Trials Directory compliance:**

- The primary purpose for the protocol is to develop a universal lymph node detection strategy. This study evaluates if systemic injections of Zr-panitumumab in conjunction with panitumumab-IRDye800 can be used to identify tumor-loaded lymph nodes to expand the capabilities of non-invasive and intraoperative cancer imaging.
- The interventional model is **Sequential**.
- There are **2 cohorts**. Both cohorts will receive the same treatment
- The study is **open-label**. No masking is used.
- The study is **non-randomized**.
- The primary outcome is **the number (proportion) of lymph nodes determined to be tumor-positive by histological and/or pathological evaluation that were predicted to be tumor-positive by Zr-panitumumab PET/CT imaging**.
- The secondary outcome is **the number (proportion) of lymph nodes determined to be tumor-positive by histological and/or pathological evaluation that were NOT predicted tumor-positive by Zr-panitumumab PET/CT imaging**.

The study is an open-label pilot study to determine the efficacy of Zr-panitumumab in tumor-loaded node detection in subjects with HNSCC that undergo surgery with curative intent. It is anticipated that 14 subjects will be enrolled into the study. Subjects will be enrolled to the node negative (no suspicion of tumor-positive lymph nodes in the neck; cN0) or node positive (suspicion of tumor-positive lymph

nodes in the neck; cN+) group based on the preoperative work-up, which includes a physical exam and evaluation of the pre-existing imaging data.

All subjects will receive a dose of 30 mg panitumumab-IRDye800. Subjects will subsequently receive 1 mCi +/- 20% of Zr-panitumumab. If at any point after infusion, 2 subjects experience a DLT (Grade 2 or greater toxicity), then the study will stop, and safety data will be reviewed.

The known rate of infusion reactions of panitumumab is 1% (package insert); therefore, we expect a DLT rate of approximately 1% or higher with panitumumab-IRDye800 or Zr-panitumumab. The probability of observing two or more DLTs within a 10-subject cohort (requiring stopping the study) is 0.4%; if the DLT rate is as high as 5%, the probability of 2 or more DLT is 8.6%.

For an overview of the proposed study, see Study Schema (page 9), and the dosing schedule below. Briefly, subjects will undergo F-FDG-PET prior to study enrollment, as is standard of care. Administration of panitumumab-IRDye800 will occur by IV over 15 minutes, followed by a 30-minute observation period. Administration of Zr-panitumumab will occur by IV, per radioactive drugs administration policies. The subjects will be observed for 1 hour following the Zr-panitumumab injection.

After infusion of study agents on Day 0, subjects will undergo Zr-panitumumab PET/CT imaging. One scan will be performed at any time starting on Day 0 (after end of observation period post Zr-panitumumab administration) and until the day before surgery (inclusive). Subjects enrolled in the dosimetry sub-study will undergo three scans, performed at any time starting on Day 0 (after end of observation period post Zr-panitumumab administration) and until the day before surgery. If available, the scans will be performed on Day 0, Day 1 and on the day before surgery.

Subjects will undergo surgical resection 2-5 days after infusion of study drugs. Imaging will be performed intraoperatively using a novel beta probe and/or high-energy gamma probe (see Appendix C for a list of devices) and the optical imaging devices (see Appendix B for a list of devices), to assess the tumor and lymph node(s) prior to resection, and the wound bed after surgical removal. The surgery will be conducted in the standard of care, and the surgeon will not use the imaging data to make decisions.

*Ex vivo*, imaging of the specimens prior to pathological assessment will be performed using non-invasive imaging modalities that do not violate or destroy the tissue. These may include beta probe and/or high-energy gamma probe, an open-field imaging system, a closed-field imaging system and a fluorescence flatbed scanning device (see Appendix B and C for a list of devices). Additionally, a closed Cherenkov imaging system may be used to image the specimen after removal (see Appendix C). Methods have been described in detail in the literature (20-25).

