6. A serum pregnancy test will be obtained on all women of childbearing age at baseline; a urine pregnancy test will be performed on Day 0 if the result of a serum pregnancy test within 72 hours before administration of panitumumab-IRDye800 is not available.
7. Blood samples for serum level of panitumumab-IRDye800 antibody and unconjugated dye, and  $^{89}\text{Zr}$ -panitumumab antibody will be drawn as follows: on Day 0 prior to panitumumab-IRDye800 infusion and at the end of the 1-hour ( $\pm 10$  mins) observation period after completion of injection of  $^{89}\text{Zr}$ -panitumumab; on Day 1-4 (only one sample will be collected on the same day when the PET/CT will be performed); on Day of surgery and on Day 15. The Day 15 time point will be 15 days  $\pm$  4 days, but is abbreviated as Day 15 throughout the protocol.
8. Blood will be collected on Day 0 prior to panitumumab-IRDye800 dose and on Day 15 and banked for future immunogenicity testing. Immunogenicity testing time points will not vary with dose.
9. Panitumumab-IRDye800 infusion to be given over 15 ( $\pm 5$  mins) minutes followed by 30 minutes ( $\pm 10$  mins) observation period.
10.  $^{89}\text{Zr}$ -panitumumab administered as a bolus injection to be done after the end of the observation period after panitumumab-IRDye800 infusion; will be followed by 1 hour ( $\pm 10$  mins) of observation period.
11. Surgical excision will be performed 2-5 days after the infusion of the study drugs.
12. A  $^{89}\text{Zr}$ -PET/CT scan will be acquired after injection of  $^{89}\text{Zr}$ -panitumumab. One scan will be performed at any time starting on Day 0 (after end of observation period post  $^{89}\text{Zr}$ -panitumumab administration) and until the day before surgery (inclusive). Subjects enrolled in the dosimetry sub-study will undergo three scans, performed at any time starting on Day 0 (after end of observation period post  $^{89}\text{Zr}$ -panitumumab administration) and until the day before surgery (inclusive); if available, the scans will be performed on Day 0, Day 1 and on the day before surgery.
13. A standard of care  $^{18}\text{F}$ -FDG-PET scan acquired within year from the day of study drug infusion is acceptable, even if this scan was/is acquired outside of Stanford.

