## **10. MEASUREMENTS**

### **10.1 Primary Outcome Measure**

**The number (proportion) of lymph nodes determined to be tumor-positive by histological and/or pathological evaluation that were predicted to be tumor-positive by  $^{89}\text{Zr}$ -panitumumab labeling.**

We will compare the number and location of  $^{18}\text{F}$ -FDG-avid nodes within the regional lymphatics to the number and location of  $^{89}\text{Zr}$ -panitumumab-avid nodes in relation to the postoperative neck dissection histopathology (gold standard).

**Outcome Measure:** Preoperatively, the location and number of  $^{18}\text{F}$ -FDG-avid nodes as well as the number and location of  $^{89}\text{Zr}$ -panitumumab-avid nodes will be determined by 2 board-certified Nuclear Medicine physicians ([name] and [name]). Once all radioactive and fluorescent nodes are removed intraoperatively, standard of care will be

performed via completion neck dissection. The excised tissue specimens will be sent to pathology where the tumor status of the lymph nodes will be determined (histology serves as our gold standard). This will allow us to determine true and false positive and negative tumor values for Zr-panitumumab and F-FDG in identifying the tumor-loaded lymph nodes.

**Time Frame:** Final false positive and negative rate, sensitivity and specificity of sentinel node detection using Zr-panitumumab can be determined towards the completion of the trials (once all subjects have been included and all the data has been collected).

**Safety Issue:** No

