Following the standard of care evaluation of PET/CT scans, maximum standard uptake values ( $\text{SUV}_{\text{max}}$ ) will be calculated for the accumulation of  $^{89}\text{Zr}$ -panitumumab in tumor tissue and/or lymph nodes. As background reading, the  $\text{SUV}_{\text{max}}$  of the mediastinum will be determined.  
Tentative cutoff for 'imaging positive': an  $\text{SUV}_{\text{max}}$  value of the lymph nodes of minimally  $1.4 \times$  the background (mediastinum). In all cases, (histo-) pathology serves as the gold standard for "true" positive / negative lymph nodes. Subsequently an ROC curve will be generated whereby we will select the point of highest specificity and sensitivity and from there we will determine if our tentative cutoff was valid or if we need to adjust.
- *Comparison fluorescence and radioactivity-based findings:*  
All tissues that will be excised during surgery will be evaluated for the presence of radioactivity and fluorescence and scored as such being positive / negative. Evaluated tissues are either 1) fluorescent only; 2) radioactive only; 3) both radioactive and fluorescent; or 4) neither radioactive nor fluorescent. This will be done quantitatively (Y/N approach) and qualitatively (see above).
  - Because the antibody is the same, only the label (IRDye800 or  $^{89}\text{Zr}$ ) differs, we expect that tissue samples that are radioactive are also fluorescent and vice versa. However, this is something that will be investigated in this study.

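### The same two physicians determine the FDG-avid and the 89Zr-avid nodes, and nothing masks either read to the other scan or to the cohort label

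*Combined protocol and SAP*

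**What the plan says.** - **Readers.** Section 10.1 (Primary Outcome Measure) covers both tracers in one sentence: preoperatively, the number and location of FDG-avid nodes and of 89Zr-avid nodes "will be determined by 2 board-certified Nuclear Medicine physicians". Section 10.2 repeats the procedure without naming readers.
- **Masking.** The registry-compliance list in section 2.4 calls the study open-label and adds "No masking is used". Sections 2.4, 10.1, 10.2 and 12 set no reader masking, reading order or separate sessions.
- **FDG scan.** It is obtained "prior to study enrollment, as is standard of care" (section 2.4). Under Table 5, footnote 13, a scan is usable if "acquired within year from the day of study drug infusion is acceptable, even if this scan was/is acquired outside of Stanford".
- **Cohort label.** Subjects enter the cN0 or cN+ "group based on the preoperative work-up, which includes a physical exam and evaluation of the pre-existing imaging data" (section 2.4).
- **Positivity rule.** For 89Zr, sections 2.4 and 12 give a tentative rule: node SUVmax at least 1.4 times the mediastinum. After an ROC analysis against pathology, "from there we will determine if our tentative cutoff was valid or if we need to adjust". No numeric cut-off is given for FDG.
- **Analysis.** Section 12 compares sensitivity and specificity of the two tracers with Durkalski's matched-pair test, and measures their association with the Phi coefficient.

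**The concern.** A matched-pair comparison of two imaging tests is meant to compare what each test shows by itself. If a reader making one call knows the other scan, the second call partly reports the first. The cohort label is a second route for the same information, because existing imaging helps to set it.

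The matched-pair test draws its evidence from nodes on which the tracers disagree, and an equivocal focus on one scan that is clear on the other is where knowledge of the other scan is most likely to change a call. Section 10.2 also singles out nodes that are FDG-positive and/or fluorescent but show no 89Zr uptake, so this affects the secondary outcome too. If reads are not independent, a reported difference or a reported agreement cannot be separated from the way the scans were read, and no later analysis can undo that.

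**Working it through.** **1. The plan's own figures.** Section 12 gives 14 subjects × 30 nodes = 420 nodes and an intra-class correlation of 0.005. Effective sample size = 420 / (1 + 29 × 0.005) = 420 / 1.145 = 366.8, matching the stated 367. At 7.5% prevalence this is 27.5 effective positive nodes. A one-sided exact McNemar test at 0.05, with 30% discordance and a 0.25 difference, has 71.4% power with 27 nodes and 73.6% with 28, matching the stated figure of more than 71%. Masking changes none of these numbers.

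**2. Weight of one call.** Expected positive nodes: 0.075 × 420 = 31.5. One altered call moves sensitivity by 1 / 31.5 = 3.2 points. Expected negative nodes: 0.925 × 420 = 388.5. One altered call moves specificity by 1 / 388.5 = 0.26 points. These are weights of a single node, not estimates of bias.

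**3. What carried-over calls do.** This is an illustration; the share b is assumed, because the documents give no value. Take section 12's 30% discordance and its lower sensitivity of 0.70, and suppose both tracers truly have that sensitivity. Among positive nodes the four cells are then: both positive 0.55, only 89Zr positive 0.15, only FDG positive 0.15, neither 0.15. Suppose the 89Zr reader upgrades a share b of the FDG-only nodes:

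- observed 89Zr sensitivity = 0.70 + 0.15b
- discordance = 0.30 − 0.15b
- Phi is recomputed from the four cells. At b = 0 it is (0.55 × 0.15 − 0.15 × 0.15) / (0.70 × 0.30) = 0.06 / 0.21 = 0.29. At b = 0.5 it is (0.625 × 0.15 − 0.15 × 0.075) / √(0.775 × 0.225 × 0.70 × 0.30) = 0.0825 / 0.1914 = 0.43.

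The last column is the chance that a one-sided exact McNemar test at 0.05 on 28 effective nodes declares 89Zr more sensitive.

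| b | 89Zr sensitivity | Discordance | Phi (positive nodes) | False finding for 89Zr |
|---|---|---|---|---|
| 0 | 0.70 | 0.30 | 0.29 | 2.1% |
| 0.25 | 0.74 | 0.26 | 0.35 | 4.5% |
| 0.5 | 0.775 | 0.225 | 0.43 | 9.5% |
| 0.75 | 0.81 | 0.19 | 0.52 | 20% |
| 1 | 0.85 | 0.15 | 0.64 | 41% |

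With a two-sided test the last column is 1.0% at b = 0, 5.0% at b = 0.5 and 24% at b = 1.

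**4. The other direction.** The same habit in negative nodes imports FDG false positives. With equal true specificity of 0.70 and 30% discordance, observed 89Zr specificity = 0.70 − 0.15b: 0.66, 0.625, 0.59 and 0.55 for b = 0.25, 0.5, 0.75 and 1. If calls are carried from 89Zr to FDG instead, the same arithmetic applies with the tracers exchanged.

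**The case against.** **The masking statement is not about readers.** It sits in a registry list between the open-label and non-randomized entries, in a study where everyone receives the same agents. A reader might take it as a decision to read PET unmasked. It does not say that. The point rests on the silence of section 10.1, where the primary outcome is defined.

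**Acquisition order is not reading order.** Because FDG is acquired before enrolment, a reader might infer that only the 89Zr read can borrow and that the bias therefore favours 89Zr. The documents do not support this. Section 10.1 gives no reading order, and FDG scans may be outside scans up to a year old, so their study read could fall near or after the 89Zr scan. Steps 3 and 4 also show that borrowing can help or harm 89Zr. Nor does section 10.1 say expressly that each physician reads both tracers. That is the natural reading, and nothing prevents it.

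**Safeguards exist.** Reads are preoperative, so they precede pathology; the surgeon does not use the imaging for decisions; and 89Zr positivity has a quantitative rule. These help in part. Preoperative reading masks pathology only. The 1.4 × rule is tentative, and a reader must still decide which focus is a node and where it lies. That the cut-off may be adjusted after the ROC analysis is a separate matter, which masking would not cure.

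**This is a small early-phase pilot.** That limits the severity. It does not remove the point, because the plan performs a formal paired test at the 0.05 level.

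**Conclusion.** The point holds as a gap in reader independence. The plan assigns both tracers' node calls to one pair of readers, masks neither read to the other scan or to the cohort, and then tests the paired difference. Following it as written can shrink discordance, inflate Phi, and move 89Zr sensitivity up or its specificity down.

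The magnitude and net direction cannot be derived from the documents. The firm figure is the weight of one call: 3.2 points of sensitivity, given 31.5 expected positive nodes, against a planned difference of 25 points. A reader might multiply it by some number of altered calls and treat the product as the expected bias. No such number is in the documents. The table in the working rests on an assumed share, equal true accuracy of 0.70, 30% discordance, and a McNemar test on 28 effective nodes in place of Durkalski's test. It shows how the comparison responds and does not predict the result.

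This should be corrected before the reads are made.

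**What to change.** Add to section 10.1 that:

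- the same two readers make the FDG and the 89Zr study reads in separate sessions;
- each read is masked to the other tracer's images and report and to the cN0/cN+ label;
- node-level calls are time-stamped and locked before surgery, for example with the FDG study read locked before the 89Zr scan is opened.

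Do not require random case order for these reads. The 89Zr scan may fall on the day before a Day 2 to 5 operation, and the synopsis expects 14 subjects over 12 to 18 months, so there will usually be only one 89Zr case waiting. If random order is wanted, use it in a batched re-read after accrual, masked to pathology and to the other tracer.

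Treatment stays open-label. The cost is reading logistics, including study reads of outside FDG scans, which section 10.1 already implies. Some recall will remain because the readers are the same, and the research reads lose some clinical context. No extra readers or scans are needed, and sample size, alpha and power do not change.
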